4.4 Premature Termination Of Study/Closure Of Center

The sponsor has the right to close this study, and the investigator/sponsor has the right to close a center, at any time, although this should occur only after consultation between involved parties. The Ethics Committee/Institutional Review Board (EC/IRB) must be informed. Should the study/center be closed prematurely, all study materials (except documentation that has to remain stored at site) must be returned to the sponsor. The investigator will retain all other documents until notification given by the sponsor for destruction.

4.5 Treatments

4.5.1 Treatments To Be Administered

This study is designed with two blinded treatment groups (C1INH vs. Placebo). Each group will include 35 patients in a treatment arm and 35 patients in a placebo arm.

This design is statistically powered to show significant differences if there is a 30--50% reduction in the treatment group and may trend towards positive treatment effect since extensive DGF (40--50%) is expected in ECD and DCD recipients. The dose of C1INH chosen is (50U/kg) (round to the nearest 500unit) X2 (high-dose treatment) which should increase serum C1INH levels significantly above physiologic levels. This is based on our observations from our experience using C1INH vs. placebo to prevent antibody-mediated rejection in humans. In those randomized to placebo, an equivalent volume of placebo (0.9%) normal saline) will be administered prior to graft reperfusion.

Patients who fulfill all I/E criteria will be enrolled into this Phase I/II study.

4.5.2 Identity Of Investigational Product(s)

Medication will be labeled according to the requirements of local law and legislation. Label text will be approved according to agreed CSL-Behring procedures, and a copy of the labels will be made available to the study site upon request.

Product name: Berinert® / C1INH (Human)

Chemical name: Complement Factor 1 Inhibitor (C1INH)

Study Medication & Dosing: Berinert® is available in a single-use vial that contains 500 units of C1 esterase inhibitor as a lyophilized concentrate. Each vial must be reconstituted with 10 mL of diluent (sterile water) provided. Prior to reconstitution, Berinert® should be stored at 2° to 25°C. After reconstitution, administration may begin within 8 hours provided the solution has been stored at up to 25°C. Berinert® is dosed at 50 units per kg body weight (round to the nearest 500units) and is administered by slow IV injection at a rate of approximately 4 mL per minute. Participation patients will receive 50U/kg C1 INH vs placebo (0.9% NS) on days 0 and day 1 post-transplant, (see Appendix A).

4.5.3 Method Of Assigning Subjects To Treatment Groups

Patients will be randomized into treatment/placebo arms in a 1:1 ratio. Randomization will be completed prior to patient entering the operating room for transplantation.

This study is a double-blind, placebo-controlled study. The clinical pharmacist will maintain the randomization assignment.

The Investigators, other study personnel, patients, and the Sponsor will be blinded to treatment assignment.

4.5.4 Selection Of Doses In The Study

4.5.4.1 Berinert® (C1INH Dosing)

For the planned study, subjects will receive C1NH 50U/kg (round to the nearest 500units) (maximum dose: 4000U) pre-operatively over a period of 10-20 minutes at any one point in time, from time of induction of anesthesia up to the beginning of renal vein anastomosis before graft reperfusion. For all dose reconstitution, Berinert® is provided in single dose vials of 500 units. Each vial will be reconstituted in 10 ml sterile water for injection). Placebo will be administered in an identical volume. An additional dose of Berinert® (50U/kg,actual body weight, maximum dose 4000U) vs. placebo will be administered at 24 hours post-surgery.

4.5.4.2 Placebo Dosing

The placebo used in this study will be 0.9% normal saline administered as a single intravenous infusion intra-operatively over a period of 10-20 minutes pre-operatively at any one point in time, from time of induction of anesthesia up to the beginning of renal vein anastomosis before graft reperfusion. The total volume will be identical to that calculated for Berinert® infusions.

4.5.5 Immunosuppression

Immunosuppression regimen is an important part of the care for recipients of kidney transplantation. The regimen to be used in this study is reflecting the fact that the patients enrolled into this study are at high risk for developing poor or delayed graft function.

4.5.3.1 4.5.5.1 Induction Antibody Therapy

All patients enrolled into this study will be treated with induction antibody therapy with Thymoglobulin® OR Campath 1H. For Thymoglobulin®, the first dose will be given immediately after the transplantation procedure to follow with additional doses so that patients receive up to 6 mg/kg (1.5mg/kg/dose) using standard institutional treatment guidelines for use of this agent in this patient population. Campath 1H will be administered in a single 30 mg subcutaneous dose post-

transplant. No induction administration of IL-2 receptor inhibitors is permitted in this protocol.

4.5.5.2 Maintenance Immunosuppression

4.5.5.2.1 Calcineurin Inhibitors (Tacrolimus or Cyclosporine)

Tacrolimus (Prograf) and Cyclosporine (Neoral) are indicated for the prophylaxis of organ rejection in patients receiving allogeneic kidney transplants. Tacrolimus or Cyclosporine will be held in this study for a minimum of 24 hours post transplant and will be initiated and monitored with trough levels using standard institutional treatment guidelines for use of these agents in this patient population.

4.5.5.2.2 Mycophenolate Mofetil (MMF)

Mycophenolate mofetil (MMF, CellCept), the morpholinoethylester of mycophenolic acid, has been shown to have antiproliferative effects on lymphocytes by blocking proliferation of T- and B-lymphocytes. MMF will be dosed using standard institutional treatment guidelines for use of these agents in this patient population. Myfortic can be used instead of CellCept and will be dosed using standard institutional treatment guidelines for use of these agents in this patient population.

4.5.5.2.3 Corticosteroids

Corticosteroids will be administered using standard institutional treatment guidelines for use of these agents in this patient population.

4.5.6 Anti-infective Prophylaxis

Valgancyclovir for the prophylaxis of CMV infection will be use for a minimum of 6 months.

Ciprofloxacin will be administered at 250mg/daily X30 days for meningococcal prophylaxis.

Local standards of care for post-transplant bacterial and fungal prophylaxis will be applied using standard institutional treatment guidelines for use of these agents in this patient population.

CONFIDENTIAL

CONFIDENTIAL

4.5.7 Selection And Timing Of Dose For Each Subject

The active treatment arm (Berinert® 50U/kg, maximum dose 4000U) will be compared to a placebo control treatment arm, with a total of 35 adult subjects in each study group. A total of 70 adult subjects will be enrolled in the study and additional subjects will not be enrolled to replace dropouts. This design is statistically powered to show differences in DGF with a 30-50% reduction in DGF predicted for the Berinert® study group. Treatment effect will be investigated following intravenous treatment with two doses of Berinert® or an equivalent volume of placebo (0.9% normal saline) pre-operatively prior to graft reperfusion and repeated 24 hours post-transplantation.

4.5.8 Blinding

The pharmacist will be contacted by the study staff and informed of a patient's eligibility. The pharmacist will prepare the blinded study medication or placebo. The study treatment will be prepared according to a pharmacist-supplied randomization code (blinded from all other study personnel). The study treatment will be prepared in an IV syringe (total volume up to 70 ml Berinert® {4000U} for 80kg individual) and labeled with:

- Protocol Number
- Screening number
- Randomization number.

The blinded intravenous syringe of study treatment labeled as stated above will be transported to the surgical suite and matched with the matching patient chart.

In case of a medical emergency, the study drug assignment for a particular patient may be unblinded. Unblinding study drug assignment will only be necessary if knowledge about treatment is needed for the medical management of the patient. The patient's treatment assignment can be identified for unblinding purposes by calling the Investigational Pharmacist [contact]). When this is necessary, the investigator must immediately notify the Sponsor's Medical Monitor, and document the reason and date of the un-blinding. The event must also be documented on the study termination record, the AE page of the CRF, and in source documents. Additionally, the Principal Investigator will submit to the Sponsor a written explanation describing the event within 5 working days. The procedures for un-blinding study drug treatment will be provided to the Principal Investigators prior to study implementation.

4.5.9 Treatment Compliance

There are only two application of the drug, which takes place approximately 60-120 minutes prior to graft reperfusion administered pre-operatively and 24 hours post-transplant.

4.6 Study Variables

4.6.1 Efficacy Variables

4.6.1.1 Primary Efficacy Endpoints

For patients who do not require dialysis in the first 7 days:

- Proportion of patients enrolled with serum creatinine >3mg/dL on postoperative day 5.
- Proportion of patients with serum creatinine reduction ratio of < 30% from 24 to 48 hours post-transplant.

For patients who require dialysis in the first 7 days: (Excluding patients who get dialysis for hyperkalemia)

- The proportion of patients enrolled who require at least one session of dialysis in the first 7 days post transplant.
- Number of dialysis sessions per patient in the first 7 days post transplant.

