2.1 Study Objectives

In this study, we propose to investigate the application of preoperative and post-transplant doses of C1INH (Berinert®)vs. placebo in adult subjects receiving a deceased donor renal allograft considered at high-risk for IRI and DGF. We hypothesize that C1INH treated patients will demonstrate improved function of the kidney allograft compared to placebo, with equivalence in safety. We will also evaluate biopsies at transplant in all entered patients.

The primary objectives of this study are: Using a double blinded, placebo controlled format, we will:

- 1. Evaluate and compare the safety of C1INH (50 U/kg, round to the nearest 500unit) administered pre-transplant and 24 hrs post-transplant in recipients of kidney allografts from high risk deceased donors. The secondary objectives are to:
- 1. On the basis of safety and efficacy, determine appropriate Berinert® study dose for Phase III investigation, and
- 2. Determine appropriate endpoint choice for Phase III investigation.

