4.6.1.2 Secondary Efficacy Endpoints

- Daily serum creatinine for seven days post transplant or until discharge.
- Daily Calculated Creatinine Clearance for seven days post transplant or until discharge.
- Serum creatinine at 14, 28, 60, and 90 days post transplant.
- Total urine output in hours 16-24, 40-48 post transplant.
- Rate of dialysis use at 14, 28, 60, and 90 days post transplant.
- Dialysis duration at 14, 28, 60, and 90 days post transplant.
- Calculated creatinine clearance at 14, 28, 60, and 90 days post transplant.

CONFIDENTIAL

- Rate of acute cellular and antibody mediated rejection episodes by day 90.
- Patient and graft survival by day 90.
 - Protocol renal transplant biopsy at time of implantation.
 - Incidence of DGF as categorized by a DGF scale of increasing severity as follows:

Grade 1 - immediate urine production and no need for dialysis with creatinine reduction ratio (CRR) between time 0 of transplantation and day 7 post-transplantation >70%

Grade 2 - creatinine reduction ratio (CRR) between time 0 of transplantation and day 7 post-transplantation of >70% with need for dialysis

Grade 3 - creatinine reduction ratio (CRR) between time 0 of transplantation and day 7 post-transplantation <70% with no need for dialysis

Grade 4 - creatinine reduction ratio (CRR) between time 0 of transplantation and day 7 post-transplantation of <70% with need for dialysis

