4.6.4.6 Serum Creatinine Reduction Ratio

Serum creatinine reduction ratio will be calculated at 48 hours post transplant, using the formula described by Govani et al (2002).

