5.5 Confidentiality

All records identifying the subject will be kept confidential and, to the extent permitted by the applicable laws and/or regulations, will not be made publicly available.

Subject names will not be supplied to the sponsor. Only the subject number and subject initials will be recorded in the case report form, and if the subject name appears on any other document (e.g., pathologist report), it must be obliterated before a copy of the document is supplied to the sponsor. Study findings stored on a computer will be stored in accordance with local data protection laws. The subjects will be informed in writing that representatives of the sponsor, EC/IRB, or Regulatory Authorities may inspect their medical records to verify the information collected, and that all personal information made available for inspection will be handled in strictest confidence and in accordance with local data protection laws.

If the results of the study are published, the subject's identity will remain confidential.

The investigator will maintain a list to enable subjects' records to be identified.

- 6 Statistical Methods And Determination Of Sample Size
- 6.1 Statistical And Analytical Plans
- 6.2 Determination of Sample Size

The sample size calculations were based on a conservative assessment aimed to show $\sim 50\%$ reduction in DGF rates with C1INH application. Data from the Cedars-Sinai Medical Center Renal Transplant Program for DGF rates are shown below:

CONFIDENTIAL

	Transplants 7/1/2011 until 7/1/2013
	N=237
	DGF Rate
ECD	27/36 (75%)
DCD	9/13 (69%)
Final Cr >/=1.5	28/37 (76%)
Non-ECD/DCD/Cr<1.5	33/100 (33%)

Briefly, the DGF rates at our center for the proposed study groups are >70% compared to 33% for SCD donors. Thus, a conservative proposal is explored below. The sample size calculations showing 35 subjects per group would sufficiently power the study (80%) to show 50% reduction when an anticipated DGF rate of 50% for the study group is anticipated.

The "proportion" below is the proportion with DGF. A 2-sided test (to be more conservative) was performed. We assumed a 50% DGF rate in the Placebo group. Treated group DGF rate vary: 20%, 25%, and 30%. sample size per group for 80% and 90% power are shown.

Two group continuity corrected χ^2 test of equal proportions (odds ratio = 1) (equal n's)

-	1	2	3	4	5	6
Test significance level, \Box	0.050	0.050	0.050	0.050	0.050	0.050
1 or 2 sided test?	2	2	2	2	2	2

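### The primary 24-48 h creatinine reduction ratio enters the plan only as the share below 30%; no listed endpoint compares it on its full scale, at a power cost that depends on assumptions

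*Combined protocol and SAP*

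**What the plan says.** Section 4.6.1.1 and the synopsis list, under the heading "For patients who do not require dialysis in the first 7 days", the primary endpoint "Proportion of patients with serum creatinine reduction ratio of < 30% from 24 to 48 hours post-transplant". Section 4.6.4.6 describes the underlying quantity: "Serum creatinine reduction ratio will be calculated at 48 hours post transplant", by a formula taken from a cited study.

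The secondary list in 4.6.1.2 uses a reduction ratio only inside the DGF grading. There it covers a different interval and is again cut, for example "creatinine reduction ratio (CRR) between time 0 of transplantation and day 7 post-transplantation <70% with no need for dialysis". The same list contains "Daily serum creatinine for seven days post transplant or until discharge" and daily calculated creatinine clearance, both on their own scales.

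Section 6.1 has a heading and no text. The synopsis says only that results will be described and compared. Section 6.2 deals with DGF alone and gives no rate, mean or SD for the reduction ratio. Section 2.1 includes the secondary objective "Determine appropriate endpoint choice for Phase III investigation".

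**The concern.** A patient whose ratio is 29% is scored the same as one whose creatinine rose, and a patient at 31% the same as one at 70%. The trial has 35 patients per arm, dropouts are not replaced (section 4.5.7), and this endpoint uses only the undialysed part of each arm. Reducing a measured value to two classes in groups this small usually costs power, and here the full value is already in hand.

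The empty section 6.1 does not remove the problem. The endpoint itself is defined as a proportion, so any method later written there would analyse a proportion.

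The choice of a Phase III endpoint is also at stake. If only the cut form is planned, a full-scale comparison made after unblinding would be post hoc, and the two forms would not stand as equal candidates.

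**Working it through.** **The plan's own figure.** Section 6.2 states no power for the reduction ratio. Its power statement concerns DGF: "The sample size calculations showing 35 subjects per group would sufficiently power the study (80%) to show 50% reduction", with "We assumed a 50% DGF rate in the Placebo group". For 50% versus 25%, two-sided 5%, 80% power:

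- Uncorrected n = [1.960 × √(2 × 0.375 × 0.625) + 0.842 × √(0.25 + 0.1875)]² / 0.25² = 57.7.
- Continuity-corrected n = (57.7/4) × [1 + √(1 + 4/(57.7 × 0.25))]² = 65.4, so 66 per group.

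This matches the plan's table. With 35 per group the corrected test has 48.1% power, not 80%. That is a separate matter. It is noted here because section 6.2 cannot be read as powering the ratio endpoint.

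**Inputs for the ratio endpoint.**

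- 35 per arm, 1:1, two-sided 5% (sections 4.5.3, 4.5.7, 6.2).
- Undialysed patients implied by DGF of 50% and 25%: 35 × 0.50 = 17.5 and 35 × 0.75 = 26.25, taken as 17 and 26.
- Assumed: the ratio is normal with equal SD, and the shares below 30% are 50% on placebo and 25% or 30% on treatment. These shares are borrowed from the DGF rates because the documents give none for the ratio.
- Implied shift in SD units, d = z(placebo share) − z(treated share): 0 − (−0.674) = 0.674 for 25%, and 0.524 for 30%.

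**Closed-form check, 17.5 versus 26.25, 50% versus 25%.**

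- Cut at 30%, uncorrected: pooled share = (8.75 + 6.5625)/43.75 = 0.35. The null SE is √[0.35 × 0.65 × (1/17.5 + 1/26.25)] = 0.147, and the alternative SE is √(0.25/17.5 + 0.1875/26.25) = 0.146. Power = Φ[(0.25 − 1.96 × 0.147)/0.146] = 39.6%.
- Full scale, z approximation: power = Φ[0.674/√(1/17.5 + 1/26.25) − 1.96] = 58.9%; the t-test gives 57.0%.

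**Simulation, 17 versus 26** (6,000 to 8,000 trials per case; ranges are between repeat runs).

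| Shares below 30% | Pearson | Continuity-corrected | Wilcoxon | Gain over Pearson | Gain over corrected |
|---|---|---|---|---|---|
| 50% vs 25% | 39-40% | 29-30% | 53% | 13-14 | 23-24 |
| 50% vs 30% | 26-28% | 18-19% | 35-36% | 7-9 | 16-17 |

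**How far the gain can shrink.**

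- Heavy tails (t, 3 df), 17 versus 26: Wilcoxon gains about 2 to 6 points over Pearson, while the t-test falls below Pearson.
- DGF of 70% and 35%, near the centre rates in section 6.2, leaves about 10 versus 22 patients (35 × 0.30 = 10.5; 35 × 0.65 = 22.75). With a normal ratio, Wilcoxon gains about 3 to 6 points.
- Selection: one latent graft function drives dialysis and is correlated with the ratio, treatment acts only through it, DGF is 50% versus 25%, and half of undialysed controls lie below the cut.

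| Correlation | Pearson | Wilcoxon |
|---|---|---|
| 0.4 | 7% | 6% |
| 0.6 | 8% | 9% |
| 0.8 | 12% | 14% |
| 0.95 | 17% | 22% |

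The gain here is about 0 to 5 points. With DGF of 70% versus 35% and correlation 0.6 to 0.8 it is about 0 to 1.

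**The case against.** The strongest objection is to the size. The documents give no distribution for the ratio. The 17 versus 26 cases also use the treatment effect twice: once to keep patients off dialysis, and again at full strength among those left undialysed. If treatment rescues borderline grafts from dialysis, those grafts join the treated undialysed group and dilute the contrast for either analysis. This stands, and it is why the lower end of the range is near zero.

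A reader might take the 35 versus 35 calculation (50% versus 25%: Pearson about 59%, Wilcoxon about 77%) as the cost. The documents do not support that, because the endpoint excludes dialysed patients.

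A reader might also infer that early creatinine is never analysed on its full scale. It is: daily serum creatinine is a secondary endpoint and covers the 24 h and 48 h values. It does not express the within-patient change between them, and it is not primary.

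Nor can the cut be called baseless. The introduction lists the day 2 ratio as one alternative definition without a threshold, but another alternative there includes a creatinine fall of less than 20-30%. The formula comes from a cited study that is not available here. The documents therefore show some precedent for a threshold, though no requirement to use only the threshold.

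Finally, it would go too far to say the trial cannot compare the two forms from its own data. The values will exist; what is missing is a planned comparison.

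It is also fair that safety is the primary objective and efficacy is described as limited in this Phase I/II study. That lowers the weight of the point but does not remove it, since the change is nearly free.

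**Conclusion.** The point holds in a limited form. The 24-48 h reduction ratio is available for each patient, is used only as the share below 30%, and is compared on its full scale by no listed endpoint.

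The cost in power cannot be fixed from the documents. Under a normal, equal-SD ratio, 17 versus 26 undialysed patients and borrowed shares of 50% versus 25-30%, Wilcoxon gains about 7 to 14 points over Pearson and 16 to 24 over the continuity-corrected test. With selection into the undialysed group, the gain over Pearson may be only about 0 to 5 points. In these runs Wilcoxon was never materially less powerful than Pearson, so the direction is dependable although the size is not.

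The restriction to patients not dialysed in 7 days, a group formed after randomisation, limits both forms alike and is a separate issue.

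**What to change.** In section 4.6.1.1 and the synopsis, define the comparison on the 24-48 h creatinine reduction ratio in percent. Use a Wilcoxon rank-sum test with the Hodges-Lehmann difference and its 95% CI. The rank test is the safer choice because the t-test lost to Pearson under heavy tails. Keep the proportion below 30% as a supporting summary, so that both forms are planned in advance as candidates for the Phase III endpoint.

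The cost is one sentence in each place and one line of analysis, with no new data or visits. The small downside is that a difference in percentage points of the ratio is less familiar to clinicians than a proportion; reporting the proportion alongside covers that. The change does not repair the post-randomisation subset, which needs its own treatment.

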Historically DGF has been defined as the requirement for dialysis during the first week after renal transplantation, however the postoperative requirement of hemodialysis or peritoneal dialysis is not standardized and the decision to

dialyze varies from center to center and among consultants (Daly et al, 2005). More recently, efforts have been made to scientifically quantify DGF in a more stringent manner with various alternative definitions of DGF including; (1) the number of days to achieve a creatinine clearance of >10 mL/min, calculated by the Gault-Cockroft formula (Giral-Classe et al, 1998), (2) a serum creatinine level of >3 mg/dL on the fifth day post-transplant (Humar et al, 2000), (3) the need for dialysis within 72 hours after transplantation (Hetzel et al, 2002), (4) serum creatinine level changes, including an increase, remaining unchanged, or decreasing by less than 10% per day immediately after surgery during three consecutive days for >1 week (Boom et al, 2000), (5) a rising serum creatinine level above that before surgery, or urine output of <300 mL within 6 hours of transplantation, despite diuretics and adequate volume (Gonwa et al, 2002), (6) urine output of <1 L in the first 24 hours or a decrease in serum creatinine of <20-30% reflected in a poor glomerular filtration rate (GFR) (Halloran and Hunsicker, 2001), and (7) calculating the creatinine reduction ratio on day two following surgery (Salahudeen et al, 2004). However despite these alternative suggestions, the conventional definition of "requirement for dialysis in the first week post-transplant" remains the most utilized and published definition for DGF, with "need for dialysis" being easily measured and clinically relevant.

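### The primary efficacy endpoints are split by first-week dialysis, the outcome C1INH is meant to change, so two do not compare the randomised arms and two have no settled denominator.

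*Combined protocol and SAP*

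**What the plan says.** Section 4.6.1.1, repeated in the synopsis (2.2), lists four primary efficacy endpoints under two headings.

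The first heading reads "For patients who do not require dialysis in the first 7 days". It covers two creatinine endpoints. One is a single-day threshold: "Proportion of patients enrolled with serum creatinine >3mg/dL on postoperative day 5". The other is an early change measure: "Proportion of patients with serum creatinine reduction ratio of < 30% from 24 to 48 hours post-transplant".

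The second heading reads "For patients who require dialysis in the first 7 days: (Excluding patients who get dialysis for hyperkalemia". It covers two dialysis endpoints. One is a yes-or-no rate: "The proportion of patients enrolled who require at least one session of dialysis in the first 7 days post transplant". The other is a count: "Number of dialysis sessions per patient in the first 7 days post transplant".

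The Introduction says that dialysis in the first week "remains the most utilized and published definition for DGF". Section 6.2 sizes the trial for a roughly 50% "reduction in DGF rates with C1INH application", with 50% assumed on placebo. Section 4.5.3 puts randomisation before entry to the operating room. Section 4.6.4.12 lets one session represent the need for dialysis and does not mention hyperkalemia. Section 6.1 is a heading without text, and the synopsis promises only descriptive and comparative statistics. No analysis population is given for these endpoints.

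**The concern.** The variable that sorts patients into the two groups is itself the outcome the drug is meant to change. A comparison within either group is therefore not protected by randomisation. If C1INH spares a patient dialysis, that patient leaves the dialysed set and joins the non-dialysed set in the C1INH arm only.

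- **Reduction ratio.** It is measured by 48 hours, but membership of its group depends on dialysis up to day 7, as much as five days later.
- **Sessions.** Among dialysed patients only, an avoided dialysis does not count as zero. It drops out.
- **Dialysis proportion.** If its heading is applied, it is 100% in both arms. It is informative only if the reference to enrolled patients overrides the heading.
- **Day-5 creatinine.** Its bullet also refers to enrolled patients. Either the heading governs and it is conditioned like the reduction ratio, or all patients are the denominator and the score of a dialysed patient is undefined.
- **Hyperkalemia.** The parenthesis can mean that patients are removed after randomisation, or that their dialysis is not counted.

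The efficacy read-out is at stake, and with it the secondary objectives in 2.1 of choosing a Phase III dose (on safety and efficacy) and a Phase III endpoint. Left open, the denominators could be settled after the data are seen.

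**Working it through.** **Inputs from the plan.** 35 patients per arm; dialysis (DGF) 50% on placebo and 25% on C1INH, the stated 50% reduction. The plan gives no creatinine, session or hyperkalemia rates, so those below are assumptions.

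**The plan's own figure.** The continuity-corrected two-sided calculation for 50% versus 25% at 80% power gives n = 65.4, hence 66 per group, as tabulated in 6.2. That calculation takes DGF as a proportion of all patients in each arm, which the headings in 4.6.1.1 do not provide.

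**Subset sizes.**

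- Non-dialysed: 35 × 0.50 = 17.5 placebo; 35 × 0.75 = 26.25 C1INH.
- Dialysed: 35 × 0.50 = 17.5 placebo; 35 × 0.25 = 8.75 C1INH.

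**Day-5 creatinine, heading applied.** Assume the drug causes no dialysis. Then 50% of patients are never dialysed, 25% are rescued by C1INH, and 25% are dialysed either way. Let q be the rate of creatinine above 3 mg/dL in the never-dialysed and r the rate in the rescued. The placebo subset rate is q. The C1INH subset rate is (0.50q + 0.25r)/0.75. With no other drug effect on creatinine, the difference is (r − q)/3.

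The last two columns show dialysis or creatinine above 3 mg/dL in all patients, assuming all dialysis precedes day 5.

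| Assumed rates | Subset, placebo | Subset, C1INH | All, placebo | All, C1INH |
|---|---|---|---|---|
| q = 20%, r = 60% | 20% | (0.10 + 0.15)/0.75 = 33% | 0.50 + 0.10 = 60% | 0.25 + 0.10 + 0.15 = 50% |
| q = r = 20% | 20% | (0.10 + 0.05)/0.75 = 20% | 60% | 0.25 + 0.15 = 40% |
| q = 30% placebo, 10% C1INH; r = 60% | 30% | (0.05 + 0.15)/0.75 = 27% | 0.50 + 0.15 = 65% | 0.25 + 0.05 + 0.15 = 45% |

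The first row reverses a benefit. The second shows no difference. The third shrinks a 20-point fall in the never-dialysed to 3 points. With no other drug effect, q from 10% to 30% and r from 20% to 80% give a subset difference (C1INH minus placebo) from −3 points, (20 − 30)/3, to +23 points, (80 − 10)/3.

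**Day-5 creatinine, all enrolled, dialysed patients scored as non-events.** With an equal 20% rate: placebo 0.50 × 0.20 = 10%, C1INH 0.75 × 0.20 = 15%. Preventing dialysis raises the failure rate.

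**Sessions.** Assume half the dialysed placebo patients have one session and half have three. The mean is 2.0 among the dialysed and 0.25 × 1 + 0.25 × 3 = 1.0 in all patients.

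- C1INH avoids only the one-session cases: 3.0 among the dialysed, 0.25 × 3 = 0.75 in all patients.
- C1INH avoids both types equally: 2.0 among the dialysed, 0.125 × 1 + 0.125 × 3 = 0.5 in all patients.

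**Hyperkalemia.** Let h be the share of dialysed patients dialysed only for hyperkalemia and p the dialysis rate. Removing them gives p(1 − h)/(1 − ph); recoding them as non-events gives p(1 − h).

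| h | Removed, placebo vs C1INH | Recoded, placebo vs C1INH |
|---|---|---|
| 10% | 47.4% vs 23.1% | 45% vs 22.5% |
| 20% | 44.4% vs 21.1% | 40% vs 20% |
| 30% | 41.2% vs 18.9% | 35% vs 17.5% |

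If hyperkalemia-only dialysis instead affects a fixed 10% of each arm, the rates are 44.4% vs 16.7% removed, 40% vs 15% recoded, and 50% vs 25% counted.

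**The case against.** The strongest reply is that the intended meaning can be recovered and that little hangs on it. The dialysis bullet refers to enrolled patients, 4.6.4.12 defines need by one session, and 6.2 sizes the trial on rates that would be impossible if the answer were 100% in both arms. The session bullet says per patient, and 4.6.4.12 counts sessions without limiting them to dialysed patients. Section 4.6.1.2 lists unconditioned daily creatinine, dialysis rate and duration, and the DGF grade scale. Safety is the only primary objective, and section 4 speaks of limited efficacy. The creatinine and session rates above are invented, and one scenario shows no bias.

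Much of this is fair. The 100% reading is the least plausible one, and an all-patient dialysis proportion is probably what was meant. For sessions, an all-patient reading may have been intended, but nothing in the text overrides the heading. The reduction ratio has no rescuing wording at all. Day-5 creatinine is not saved by an all-enrolled reading, as the 10% versus 15% example shows. The unconditioned measures are only secondary.

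Two smaller points also stand. Where the drug has no other creatinine effect, the day-5 subset bias runs against C1INH whenever rescued kidneys do worse; it is uncertain only because neither condition is known. And if hyperkalemia-only dialysis is a constant share of all dialysis, the rule hardly moves the relative effect: C1INH/placebo ratios are about 0.46 to 0.49 removed and 0.50 recoded. With a fixed 10% per arm, the ratio is about 0.38 either way, against 0.50 if counted.

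Creatinine after dialysis is hard to interpret, which may be why the split was made. Counting dialysis as failure deals with that without breaking randomisation.

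**Conclusion.** The concern holds. As written, the reduction-ratio and session endpoints do not compare the randomised arms, and the day-5 creatinine and dialysis endpoints lack a settled denominator. This follows from the text and needs no assumed rate.

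The size does rest on assumptions. At the plan's 50% versus 25%, the day-5 subset comparison can move from no bias to 23 points against an effective drug, and the session mean can read 2.0 versus 3.0 when the all-patient means are 1.0 versus 0.75. Neither size nor direction can be fixed from the documents.

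It should be corrected before analysis, because it affects every primary efficacy endpoint. Since safety is the primary objective, the severity is open to argument; the damage falls on the efficacy read-out and the choices for Phase III.

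**What to change.** Amend 4.6.1.1, 4.6.4.12 and the synopsis, and state the population in 6.1:

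- Delete both headings. Use all randomised and transplanted patients as the denominator for each primary efficacy endpoint, and report by arm anyone randomised but not transplanted.
- Report the proportion with at least one dialysis session in the first 7 days in all patients, and say that this is the DGF endpoint to which the sample size refers.
- For day-5 creatinine and the 24-48 hour reduction ratio, count dialysis, graft loss or death by the time of that assessment as failure.
- Count sessions in all patients, with zero where there were none.
- Keep patients dialysed for hyperkalemia in the denominator. Report dialysis for any indication and dialysis with hyperkalemia-only sessions recoded as non-events, state which is the main analysis, and cross-reference 4.6.4.12.
- Say how a non-dialysed patient discharged before day 5 is scored. Section 4.6.3.3 measures creatinine daily only until discharge; Appendix A adds day-7 laboratory tests after early discharge, but not day-5 tests.

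The cost is a wording amendment. Dialysis and creatinine are already scheduled for all patients, and only the early-discharge rule is new. The creatinine endpoints become composites and must be described as such. The change does not cure a separate power shortfall: the plan's table needs 66 per group for 50% versus 25%, and 35 per group gives about 48-59% two-sided power, depending on the continuity correction and method (normal approximation 48.1% corrected, 58.2% uncorrected; exact 49.8% and 58.9%).
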